6.1.2 CDC-based COVID-19 endpoint definition

The CDC-based definition of the COVID-19 endpoint is defined as symptomatic NAAT-confirmed COVID-19 based on CDC criteria, where the nucleic acid test NAAT may or may not be triggered by symptoms. The CDC-based COVID-19 endpoint is defined as the first occurrence of symptomatic NAAT-confirmed COVID-19 based on the following criteria:

- At least ONE of the following systemic or respiratory symptoms: Fever ($\geq 38^{\circ}\text{C}$), chills, cough, shortness of breath and/or difficulty breathing, fatigue, muscle and/or body aches [not related to exercise], headache, new loss of taste/smell, sore throat, congestion, runny nose, nausea, vomiting, or diarrhea; AND
- At least ONE (post-baseline) nasal swab (or respiratory sample, if hospitalized) positive for SARS-CoV-2 by NAAT.
- The symptom date and NAAT positive date must be within 14 days of each other. Specifically, if the onset of qualifying symptom(s) occurred prior to the specimen collection date of a NAAT-positive result, then the date of last reported symptom(s) must be after 14 days prior to the NAAT-positive date. If the onset of qualifying symptoms occurred after a NAAT-positive date, then the onset date of qualifying symptom(s) must be within 14 days of the NAAT-positive date.

The date of a COVID-19 endpoint according to the CDC-based definition is the **earlier** date of a qualifying symptom and the date of the first confirmatory positive NAAT that satisfy the criteria stated above.

For the Part B or the Part A+B analyses, although additional NAAT testing was performed at the M1 vaccination visit for study groups 1 & 3, not for study group 2 or 4, the randomization

between the bivalent and monovalent Month 6 boost arms was preserved within each study group. Therefore, the primary analyses in the RM6 cohort comparing between the randomized bivalent and monovalent boost arms will use the CDC1 endpoint that include NAAT testing results at Month 1. The CDC2 endpoints derived to exclude NAAT testing results at Month 1 for comparisons of COVID risk between different groups will only be applicable to the exploratory analyses that include also participants who missed the Month 6 vaccination, or received the monovalent boost outside of the randomization scheme.

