8.2.2 Exploratory analyses comparing hybrid and vaccine immunity groups among PLWH

For analyses including information from both the pre- & post-M6 stages, exploratory analyses of COVID-19 and severe COVID-19 between hybrid vs. vaccine immunity groups will consider two definitions of hybrid/vaccine immunity groups. The first is based on information at baseline and follows the same definition used in the Part A SAP for AG1 (Vaccine Immunity) and AG2.1 (Hybrid Immunity) and repeated below for easy reference.

1. AG1 (PLWH Vaccine Immunity; HIV+,SARS2-,2d) = PLWH; baseline SARS-CoV-2 naïve (negative for POCS, CLS, and NAAT); assigned 2 vaccinations pre-Month 6
2. AG2.1 (PLWH Hybrid Immunity; HIV+,SARS2+,1d) = PLWH; baseline POCS positive; assigned 1 vaccination pre-Month 6

The second definition of hybrid/vaccine immunity groups is based on a combination of baseline hybrid/vaccine immunity group information, Month 6 SARS-CoV-2 status and Month 6 recent SARS-CoV-2 infection status (see definitions in Section 5). Specifically, Month 6 Vaccine Immunity group includes a subset of AG1 participants who had no evidence of SARS-CoV-infection before or at Month 6 (i.e., Month 6 SARS-CoV-2 status = vaccine immunity); Month 6 Hybrid Immunity group includes a subset of AG2.1 participants who had no evidence of recent SARS-CoV-2 infection at Month 6 (i.e., Month 6 recent infection status = negative).

Comparing baseline hybrid vs. vaccine immunity groups among PLWH

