10.1 Cumulative-failure-time-based parameters of interest

Let T be the failure time using the study time scale (based on one of the study time origins defined above), t_0 a fixed time point of interest after the given time origin, and W baseline covariates. For a given analysis, we denote by A a binary indicator of belonging to either of strata which define the comparison groups of interest. In the primary analysis A is indicator of receiving a bivalent or monovalent M6 booster (in analyses), and it is similarly defined elsewhere. We denote by $T(a)$ the counterfactual failure time if $A = a$.

In a cumulative-incidence-based analysis, parameters of interest are the marginalized failure time

Comparing bivalent vs. monovalent booster		
Exploratory analysis I		
Target population	FAS participants receiving a M6 vaccine regardless of randomization scheme (FM6)	
Endpoint	COVE-/CDC-based/Severe (when applicable) COVID-19 endpoints counted 1 day after M6 vaccination	
Time frame	M6 vaccination to M12/M18 visit	
Exploratory analysis II		
Target population	FAS PLWH/PLWoH receiving a M6 vaccine regardless of randomization scheme (FM6)	
Endpoint	COVE-/CDC-based/Severe (when applicable) COVID-19 endpoints counted 1 day after M6 vaccination	
Time frame	M6 vaccination to M12/M18 visit	
Comparing baseline hybrid vs. vaccine immunity among PLWH		
Exploratory analysis III		
Target population	AG1 and AG2.1 receiving a bivalent M6 vaccine regardless of randomization scheme (AG1 and AG2.1 in FM6)	
Endpoint	COVE-/CDC-based/Severe (when applicable) COVID-19 endpoints counted 1 day after enrollment	
Time frame	Enrollment to M12/M18 visit	
Exploratory analysis IV		
Target population	AG1 and AG2.1 receiving a monovalent M6 vaccine regardless of randomization scheme (AG1 and AG2.1 in FM6)	
Endpoint	COVE-/CDC-based/Severe (when applicable) COVID-19 endpoints counted 1 day after enrollment	
Time frame	Enrollment to M12/M18 visit	
Exploratory analysis V		
Target population	AG1 and AG2.1 not receiving M6 vaccination regardless of randomization scheme (AG1 and AG2.1 in FM6)	
Endpoint	COVE-/CDC-based/Severe (when applicable) COVID-19 endpoints counted 1 day after enrollment	
Time frame	Enrollment to M12/M18 visit	
Comparing Month 6 hybrid vs. vaccine immunity among PLWH		
Exploratory analysis VI		
Target population	AG1 and AG2.1 receiving a monovalent M6 vaccine regardless of randomization scheme (AG1 and AG2.1 in FM6)	

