11.4.3 Exploratory comparisons

Exploratory analysis I is analogous to primary analysis I and secondary analysis I except that the analysis cohort will be the full M6 cohort (FM6). The same stratification and covariate adjustment strategies used in secondary analysis I will be adopted here.

Exploratory analysis II is analogous to the secondary analysis III except that the analysis cohort will be the FM6 PLWH/PLWoH. The same stratification and covariate adjustment strategies used in secondary analysis III will be adopted here.

Exploratory analysis III seeks to compare the COVID-19 incidence among participants in Analysis Group 1 vs. Analysis Group 2-1 (defined at baseline/enrollment) counting events from enrollment. To this end, the following Cox regression model is considered:

$$\lambda_{ji}(t | A_i, W_i) = \lambda_{0j}(t) \exp \{ \beta A_i + \beta_1 Z_i(t) + \beta_2 A_i Z_i(t) + \gamma^T W_i \} I(t > \tau_i^{\text{enroll}}), \quad (6)$$

with $A_i = 1$ if participant i is in AG 2-1 and 0 if in AG 1, and $Z_i(t)$ is a time-varying indicator of receiving a M6 booster vaccine. The analysis will consider the same stratification and covariate adjustment strategy as specified in the pre-M6 SAP. Key parameters of interest include $\exp\{\beta\}$, $\exp\{\beta_1\}$ and $\exp\{\beta_2\}$.

Exploratory analysis IV and V are analogous to exploratory analysis III and will adopt the same stratification and covariate adjustment strategies.

Exploratory analysis VI and VII are analogous to the hybrid vs. vaccine-induced comparison as specified in the pre-M6 SAP, except that the analysis will define the hybrid vs. vaccine immunity status based on M6 and count events 13 days post M6 vaccination. The analyses will adopt the same stratification and covariate adjustment strategies as its pre-M6 counterpart.

12 Multiplicity adjustment

For all analyses, point estimates, 95% CIs and nominal p-values will be displayed in forest plots without multiplicity adjustment. No multiple hypothesis testing will be done in any described analyses.

13 Handling missing data

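### Read literally, SAP 6.1.2 shuts exploratory analysis III out of the CDC2 endpoint, although III compares a group swabbed at Month 1 with one that was not

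*SAP*

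**What the plan says.** SAP 6.1.2 notes that "additional NAAT testing was performed at the M1 vaccination visit for study groups 1 & 3, not for study group 2 or 4". It then handles this unequal testing with two versions of the CDC-based endpoint:

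- **CDC1.** The primary analyses in the randomized Month 6 cohort "will use the CDC1 endpoint that include NAAT testing results at Month 1". The reason given is that randomization holds within each study group, so the extra swab is balanced between the boost arms.
- **CDC2.** The purpose is stated first: "The CDC2 endpoints derived to exclude NAAT testing results at Month 1 for comparisons of COVID risk between different groups". The scope follows in the same sentence: CDC2 "will only be applicable to the exploratory analyses that include also participants who missed the Month 6 vaccination, or received the monovalent boost" outside the randomization.

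Exploratory analysis III is set out in SAP Table 3. Its population is "AG1 and AG2.1 receiving a bivalent M6 vaccine regardless of randomization scheme (AG1 and AG2.1 in FM6"), and its endpoints are "COVE-/CDC-based/Severe (when applicable) COVID-19 endpoints counted 1 day after enrollment". Section 8.2.2 defines AG1 as PLWH who were naive on all three baseline tests and "assigned 2 vaccinations pre-Month 6", and AG2.1 as PLWH positive on the point-of-care test and assigned one dose. In the Cox model of Section 11.4.3 the group indicator is coded "with $A_i = 1$ if participant i is in AG 2-1 and 0 if in AG 1". Analyses IV and V apply this comparison to monovalent recipients and to people who had no Month 6 dose.

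**The concern.** The reason for CDC2 is that one side of a comparison had a scheduled swab that the other side did not. That matters when the comparison is between study groups and the counting window contains Month 1. The scope clause, however, turns on something else: whether the analysis includes people who missed the Month 6 dose or had monovalent outside the randomization. The two tests usually agree. In exploratory III they do not.

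Under the CDC definition the NAAT need not be prompted by symptoms, and the endpoint is dated to the earlier of symptom and positive swab. A routine Month 1 swab can therefore create a case in AG1, or bring one forward, with no counterpart in AG2.1. SAP 6.1 also makes the CDC definition the leading one. At stake are a one-directional detection bias in the CDC-based result of III, and a definition that differs from that used in its sister analyses IV and V.

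**Working it through.** The plan states no event count or power for exploratory III, so there is no figure to reproduce. The check is to apply the scope clause to each exploratory analysis in SAP Table 3 and ask whether the choice of CDC version could matter there.

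| Analysis | Contrast | Missed Month 6, or monovalent outside randomization, included? | Counting starts | CDC2 by the literal clause? | Month 1 in window? |
|---|---|---|---|---|---|
| I, II | bivalent vs monovalent | yes | after Month 6 dose | yes | no |
| III | AG2.1 vs AG1, bivalent | no | enrolment | **no** | **yes** |
| IV | AG2.1 vs AG1, monovalent | yes | enrolment | yes | yes |
| V | AG2.1 vs AG1, no Month 6 dose | yes | enrolment | yes | yes |
| VI | Month 6 hybrid vs vaccine, monovalent | yes | after Month 6 dose | yes | no |
| VII | Month 6 hybrid vs vaccine, bivalent | no | after Month 6 dose | no | no |

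A bivalent recipient neither missed Month 6 nor had the monovalent vaccine. SAP Section 2 adds that before protocol version 6.0 everyone vaccinated at Month 6 received monovalent. III therefore contains nobody of either kind named in the clause.

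SAP Section 4 takes the first event after the time origin. In I, II, VI and VII a Month 1 result precedes that origin, so CDC1 and CDC2 do not differ through the Month 1 swab. The choice matters only in III, IV and V, and the clause covers IV and V but not III.

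**Direction.** The swab exists only in AG1. It can add or advance an AG1 case and can do nothing in AG2.1, so any effect favours hybrid immunity.

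**Size, as an illustration.**

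- q, the share of AG1 NAAT positive at Month 1: not in the documents; assumed 1-4%.
- s, the share of those with a qualifying symptom: assumed about 14%, from the statement in Protocol 2.1 that 86% of pre-Month 6 cases were asymptomatic (100 - 86 = 14).
- Reference AG1 rate: 7.1% per year (Protocol 2.1, PLWH without prior infection).

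Added AG1 cases = q x s:

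- low: 0.01 x 0.14 = 0.0014, or 1.4 per 1,000
- high: 0.04 x 0.14 = 0.0056, or 5.6 per 1,000

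Relative rise = (0.071 + q x s) / 0.071:

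- low: 0.0724 / 0.071 = 1.020
- high: 0.0766 / 0.071 = 1.079

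The hybrid/vaccine ratio would be multiplied by 0.071 / 0.0724 = 0.98 to 0.071 / 0.0766 = 0.93.

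For given q and s these are upper limits, because they treat every symptomatic Month 1 positive as a new case. Protocol 9.5 elicits symptoms about every two weeks and arranges a swab for many of them. A case found that way remains in CDC2 and is not added by CDC1. A person who has a later episode is only counted earlier.

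**The case against.** The strongest reply is that the SAP never assigns III to CDC1. It names CDC1 only for the primary analyses in the randomized cohort, on a ground (randomization within study group) that cannot apply to AG1 versus AG2.1. The stated purpose of CDC2, comparing risk between different groups, fits III exactly. The clause about missed doses and off-scheme monovalent can be read as describing the exploratory analyses as a family. SAP Section 1 describes them in similar terms, Section 8.2 speaks of hybrid-versus-vaccine comparisons by booster type across all enrolled participants, and Section 8.2.2 treats III to V as one analysis repeated in three subsets. The pre-Month 6 SAP, on which Section 6 relies for its endpoint definitions, may settle the matter; it is not among the documents reviewed.

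Much of this stands. III reaches CDC1 only by elimination, and CDC2 may well have been intended. But the clause says CDC2 applies only where such participants are included, and a programmer following it would leave III out. The default CDC definition accepts any post-baseline swab, so the Month 1 result would then remain in. Section 11.4.3 takes stratification and covariates from the pre-Month 6 SAP but does not mention an endpoint version. The stated scope therefore conflicts with the stated purpose in an analysis where the choice matters.

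A reader might also infer that the three booster strata cannot be compared at all. The documents do not support that. The COVE-based endpoint is symptom-triggered (SAP 6.1.1) and severe COVID-19 builds on it (SAP 6.2), so both keep one definition across III to V. The SAP plans no formal test between these strata.

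**Conclusion.** The point holds as a conflict between the wording of the scope clause and the purpose of CDC2, confined to the CDC-based endpoint in exploratory III. If the clause is followed as written, that endpoint can gain or advance cases only in AG1, and its definition differs from IV and V. The randomized bivalent-versus-monovalent comparisons and the COVE-based and severe endpoints are unaffected. III is exploratory, needs at least 7 endpoints, and may not appear in the primary publication (SAP 8.2).

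The size cannot be derived from the documents. With 1-4% positivity and 14% symptomatic, both assumed, the rise in AG1 is at most about 2-8% relative to 7.1%, and less where symptom-triggered swabs would find the same cases. The case definition behind the 7.1% is not stated, nor are the symptom criteria behind the 86%, so the range is only illustrative.

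Two stronger readings should be resisted. One is that hybrid protection is overstated as a matter of fact: that depends on the clause being applied literally. The other is a much larger effect. Assuming 50% symptomatic with 4% positivity would give (0.071 + 0.020) / 0.071 = 1.28, but nothing in the documents supports a 50% share. Nor does the 7% NAAT positivity among point-of-care negatives in SAP Table 1 anchor q, because it is a baseline figure and AG1 excludes baseline NAAT positives.

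This should still be corrected: the bias has a known direction, it falls on the leading case definition, and it is removed at almost no cost.

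**What to change.** State in SAP 6.1.2 that, for the CDC-based endpoint, CDC2 is used in exploratory analyses III, IV and V, the hybrid-versus-vaccine comparisons counted from enrolment. If the pre-Month 6 SAP already says this for AG1 versus AG2.1, a cross-reference to it would help.

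No change is needed for I, II, VI and VII, which count from the Month 6 dose or later, or for the primary and secondary randomized comparisons.

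The cost is one sentence. SAP 6.1.2 describes CDC2 as already derived, so no new data or endpoint derivation is required.

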6.2 Severe COVID-19 endpoint

The severe COVID-19 endpoint is defined as the first occurrence of a COVE-based COVID-19 having at least one sign, symptom, or other evidence of severe disease (e.g., respiratory failure, shock, intensive care unit admission). The date of a documented/adjudicated severe COVID-19 endpoint is the later date of a symptom and the date of positive NAAT. This (event) date is supplied by the Endpoint Adjudication Committee.

6.3 SARS-CoV-2 infection endpoint

6.3.1 SARS-CoV-2 infection regardless of symptomology

Two definitions are considered for the SARS-CoV-2 any-infection endpoint regardless of symptomology. Definition 1 is the primary definition. Definition 2 is an exploratory definition.

- Definition 1: SARS-CoV-2 any-infection is defined in all participants who are:
 - baseline NAAT negative but tested NAAT positive at at least another post-baseline time-point, either triggered by symptom or performed at routine swabbing visits; OR
 - baseline NAAT positive but detected NAAT positive when either a) there are two consecutive negative NAAT results between the baseline and post-baseline positive swabs, or b) a positive post-baseline NAAT result is found at least 90 days after a single NAAT negative swab. Future analyses incorporating sequence information may also consider multiple occurrences; OR
 - baseline anti-N CLS negative but detected anti-N CLS positive post-baseline; OR
 - baseline anti-N CLS positive and detected anti-N CLS positive with anti-N IgG concentration at least 1.5 times higher than that at baseline. When the quantitative readout from the CLS assays is not available, this last criterion will not be considered.
- Definition 2: SARS-CoV-2 infection is defined only in participants with negative baseline SARS-CoV-2 status as defined in Section 5 based on the 3 tests (NAAT, POCS and CLS). A SARS-CoV-2 infection endpoint is any post-baseline SARS-CoV-2 infection detected positive by anti-N CLS, OR by NAAT (triggered by symptom, routine testing or other reasons).

6.3.2 Asymptomatic/subclinical SARS-CoV-2 infection

TBD.

6.3.3 Definition of a new infection endpoint based on genetic sequence data

TBD.

7 Part B analyses: post-M6 stage

All analyses in the post-M6 stage will start counting events either 1 or 13 days after the Month 6 vaccination date till the Month 12 visit for the Month 12 analyses, and till the final study visit at Month 18 for the final analyses. The Cox model approach will always use the calendar time scale and the cumulative incidence approach will always use the study time scale. These analyses will not adjust for multiple looks of the data (at Month 12 and Month 18) given the nature of the study being not to license a product.

7.1 Primary and secondary analyses comparing randomized bivalent vs. monovalent boost arms

For post-M6 follow-up in Part B of the study, the primary analysis is the comparison of COVID-19 risk between the monovalent and bivalent randomized arms, counting events starting 14 days after the Month 6 vaccination in the Randomized Month 6 (RM6) analysis cohort. When there are at least 7 severe COVID-19 cases, the same analysis will be repeated for the severe COVID-19 endpoint as a co-primary endpoint but without covariate adjustment due to the expected small number of severe COVID-19 endpoints. The secondary analysis involves the same comparison of COVID-19 risk and severe COVID-19 (if applicable), but counting events starting 1 day after the Month 6 vaccination in the RM6 analysis cohort. Both the primary and secondary analyses will only include participants who received the Month 6 vaccination in Version 6 under the study-group-stratified randomization scheme.

Two types of estimation procedures are used in each of the primary and secondary analyses. We consider estimation of hazard ratios using Cox proportional hazards regression, as well as estimation of absolute and relative differences in cumulative incidence of infection using methodology recently proposed by Westling et al. (2023).

Calendar-time-based Cox proportional hazards models will be employed to estimate the hazard ratio (HR) between the bivalent vs. monovalent randomized arms. The model will be stratified by the 4 study groups and region (RSA vs. other), thus allowing for a different baseline hazard for each of the $4 \times 2 = 8$ strata. Since the comparison is between randomized groups, the main analysis will only adjust for a small number of covariates that are deemed important or known to be associated with COVID-19 risk to increase efficiency in statistical inference. In particular, sex-assigned-at-birth (Female vs. Male) and baseline history of TB (yes vs. no) were found associated with CDC endpoints in Part A analyses, and having had a recent infection is expected to be associated with COVID-19 risk. Therefore, sex-assigned-at-birth, history of TB at Month 6, and recent SARS-CoV-2 infection status at Month 6 (see definition in Section 5) will be adjusted for in all primary and secondary analyses comparing randomized bivalent vs. monovalent boost arms. These analyses will also be repeated within people who live with HIV (PLWH) and HIV-negative participants, separately. For analyses among PLWH, CD4 counts (\leq vs. > 500 cells/mm 3 at Month 6) and HIV viral load (detectable vs. not detectable at Month 6) will be further adjusted for in

addition to sex assigned at birth, history of TB and recent infection status. For analyses among HIV-negative participants, a subset of the covariates maybe considered to avoid data sparsity, with recent SARS-CoV-2 status as the leading covariate to consider. Specifically, for Cox regression among HIV-negative participants (PLWoH), we will not adjust for TB status due to data sparsity.

We also make comparisons of covariate-adjusted cumulative incidence curves for each comparison arm. We provide a full description of the covariate-adjustment strategies in Section 11.3.

For both the Cox regression approach and the cumulative incidence approach, if there are fewer than 20 COVE-/CDC-based COVID-19 endpoints, then the corresponding endpoint will only be studied descriptively. In a pre-specified Cox regression analysis, if the number of endpoints is fewer than the number of covariates to be adjusted multiplied by 5, then this analysis will only be conducted descriptively. Only studied descriptively means that numbers of endpoints by treatment arm and covariate strata are reported, but no estimation or testing of treatment effect parameters is performed.

